7.9.2. Secondary Endpoints

7.9.3. TIR change over time

The objective is to assess the change of the TIR collected over the Run-in phase and over the Study phase every three months until 12 months. The Time In Range (TIR) will be assessed every 3 months.

The analysis will use multiple data points per patient (baseline, 3, 6, 9 and 12 months). The change over time will be analyzed by means of GEE (generalized estimating equation) models (or mixed models) for continuous outcomes to account for repeated measures using patient as the subject.

The dependent variable will be pre-log transformed depending on normal or non-normal distribution. The model will have the TIR as dependent variables and baseline values and visits. All assumptions for regression models will be assessed by viewing plots of the residual values. Mean with standard errors at each time point will be reported for the TIR and for graphical purpose only separately by population as deemed appropriate.

The adjusted mean change will be displayed together with their 95% confidence interval (95%CI).

7.9.4. Satisfaction score based on the DTSQc

To evaluate the satisfaction score based on the DTSQc evaluated at 6 months. The different DTSQc versions will be used to assess satisfaction in the following populations:

- DTSQc Adult (≥ 18 years old)
- DTSQc Teen (13-17 years old)
- DTSQc Parent (7-12 years old)

[figure not shown]
The DTSQc has six items related to treatment satisfaction and two other items assess perceived frequency of hyperglycaemia and hypoglycaemia. Each item has a maximum of 3 (more satisfied now) and a minimum of -3 (less satisfied now) with a midpoint of 0 reflecting no change. The scale total is computed by adding all items excluding two items (2,3) on hypo/hyperglycemia which will be analyzed separately. The scale total will be reported using summary statistics for each population. All values greater than 0 will be defined as an improvement. Although this endpoint was not powered for testing, the DTSQc will be also analyzed by means of one sample Z-score test or Wilcoxon signed rank sum test according to the normal or non-normal distribution.

The scoring system for the scale total by population is the following:

DTSQc Adults: 8 items (-3/3 scores). The scale total is computed by adding 6 items (excluding two items (2,3) on hypo/hyperglycemia that must be analyzed separately), to produce the Treatment Satisfaction score which has a minimum of -18 and 18.

DTSQc Teen: 12 items (-3/3 scores). The total score is computed by adding the 10 items (2 items on hypo/hyperglycemia must be analyzed separately) to produce the Treatment Satisfaction score, which has a minimum of -30 and 30.

DTSQc Parent: 14 items (-3/3 scores). The total score is computed by adding the 12 items (2 items on hypo/hyperglycemia must be analyzed separately) to produce the Treatment Satisfaction score, which has a minimum of -36 and 36.

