The primary analysis will be performed on the Intention To Treat (ITT) set and a sensitivity analysis will be performed using the Per Protocol set including all subjects that were compliant with the protocol.

The ITT includes all patients enrolled in the study those sign Data Release Form, fulfill the inclusion and exclusion criteria. The ITT will be used for all endpoints and safety evaluation. For patients who dropout the analyses will include all data up to the point of their last data collection.

The PP includes all patients enrolled in the study those sign Data Release Form, fulfill the inclusion and exclusion criteria and having at least 70% of time using the Auto Mode. The PP set will be used for all endpoints.

The primary endpoint on efficacy defined as the change of TIR at 6 months from Auto Mode activation at baseline will be analyzed by means of paired (samples) t-test or Wilcoxon signed rank sum test according to the normal or non-normal distribution. The mean change will be displayed together with their 95% confidence interval (95%CI). Additional exploratory analysis on the TIR change over time (baseline, 3, 6 and 12 months follow-up) will be analyzed by means of mixed models for repeated measures. The dependent variable will be pre-log transformed depending on normal or non-normal distribution. The model will have the clinical outcomes as dependent variables and baseline values and visits as explanatory variables. All assumptions for regression models will be performed by assessment of plots of the residual values. Difference between visits means will be tested by applying contrast on the estimated model. The plot for the mean change over time will be

reported.

The secondary endpoint on satisfaction defined by the DTSQc will be analyzed by means of one sample Z- score test. The DTSQc has six items related to treatment satisfaction and two other items assess perceived frequency of hyperglycemia and hypoglycemia. Each item has a maximum of 3 (more satisfied now) and a minimum of -3 (less satisfied now) with a midpoint of 0 reflecting no change. The scale total is computed by adding 6 items (1,4,5,6,7,8) and the 2 items on hypo/hyperglycemia will be analyzed separately. Previous studies on patients treated with MiniMed™ 640G pump have shown a good satisfaction using the DTSQc questionnaire. The sample size estimated would also allow us to demonstrate a positive DTSQc satisfaction score.

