7.2. General Methodology

Descriptive statistics will be used to summarize patient characteristics. For categorical variables, the description will consist at least of the sample size, numbers of missing data and valid data, the frequency and the percentage of each category. Denominators for calculation of percentages will be taken as the number of subjects with available (not missing or unknown) observations in the specified patients sets and groups unless otherwise stated. Percentages will be presented with no decimal (or one decimal, if appropriate) and rounded to the nearest integer. For continuous variables, the description will consist at least of the sample size (N), number of subjects with non-missing observation (n), mean, standard deviation, standard error, minimum, median and maximum. For $n < 3$, only mean, minimum and maximum will be displayed. In general, minimums and maximums will be presented to the same level of accuracy as the raw data; means and medians will be presented to 1 further decimal place; if appropriate, standard deviation and standard error will be presented to 2 further decimal places.

Device data metrics will be derived in a real-world data setting using all the device data collected during the patient study exposure.

It is anticipated that SAS 9.4 or later (SAS Institute Inc., Cary, NC, USA) will be used to perform all statistical analyses. Statistical tests will be based on a one-sided significance level of 0.05, and possible interaction effects will be evaluated at a significance level of 0.10. No adjustments for multiple comparisons will be performed. Additional exploratory analyses will be conducted as deemed appropriate and described as ad-hoc analysis in the study report.

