7.5. Adjustments for Multiple Comparisons

No adjustments for multiple comparisons will be performed.

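### The DTSQc total is assigned a one-sample Z-test without a known SD; a one-sample t-test within each age version should replace it

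*SAP*

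**What the plan says.** SAP 7.9.4 has the DTSQc total summarised first and then tested. On the summaries: "The scale total will be reported using summary statistics for each population". On the test: "the DTSQc will be also analyzed by means of one sample Z-score test or Wilcoxon signed rank sum test", with normality deciding between the two. The section introduces the test with the caveat "Although this endpoint was not powered for testing". The reference value is 0, since items are scored "with a midpoint of 0 reflecting no change". The total runs from -18 to 18 for adults, -30 to 30 for teens and -36 to 36 for parents. SAP 7.9 fixes these three groups by age at consent.

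Protocol 12.3 also names a one-sample Z-score test ("The secondary endpoint on satisfaction defined by the DTSQc will be analyzed by means of one sample" sample, followed by the Z-score wording), but it offers no Wilcoxon alternative.

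The level comes from SAP 7.2: "Statistical tests will be based on a one-sided significance level of 0.05". Neither document states an SD for the DTSQc, a source for the denominator of the Z statistic, or an expected or minimum size for any age group.

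**The concern.** A Z-test treats the SD as known. That leaves two ways to read the plan. If a known SD is meant, none is supplied and the test cannot be run as written. If the sample SD is meant, the statistic follows a t distribution under normality, and the normal cut-off rejects too often in small samples.

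The choice is also out of line with the rest of the plan. The SAP's other paired mean-change tests (primary TIR, DQoL, HFS, HbA1c and DTSQs) all use a paired t-test or Wilcoxon, and no reason is given for treating the DTSQc differently.

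At stake is whether the one-sided 5% level holds for one secondary result. That result will be read: protocol 6.1 notes that the French health authority recommends the DTSQ forms, and protocol 12.3 expects the study to show a positive DTSQc score.

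**Working it through.** **Inputs.** One-sided level 0.05 (SAP 7.2), null value 0 (SAP 7.9.4), and no SD or group size for the DTSQc in either document. Group size n is therefore an assumption and is varied over a range.

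**The plan's own level.** With a truly known SD, the statistic is standard normal under the null and P(Z > 1.645) = 0.05. The stated level is met only in that case.

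**With an estimated SD.** Let T = mean / (s/√n), with s from the sample. For normal data with true mean 0, T has a t distribution on n - 1 degrees of freedom. The true one-sided size of the Z-test is then P(t with n - 1 df > 1.645). The last column is the cut-off that would hold 5%.

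| n in the tested group | True one-sided size | Excess over 5% (points) | Correct t cut-off |
|---|---|---|---|
| 10 | 6.72% | 1.72 | 1.833 |
| 15 | 6.11% | 1.11 | 1.761 |
| 20 | 5.82% | 0.82 | 1.729 |
| 30 | 5.54% | 0.54 | 1.699 |
| 50 | 5.32% | 0.32 | 1.677 |
| 100 | 5.16% | 0.16 | 1.660 |
| 245 | 5.06% | 0.06 | 1.651 |

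The size is at most 6% from n=17, at most 5.5% from n=33 and at most 5.1% from n=159.

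**Check on bounded integer scores.** DTSQc totals are sums of 6, 10 or 12 items scored -3 to 3, so they are not exactly normal. Simulated totals of this kind with true mean 0 gave a Z-test size of 6.6% to 6.9% at n=10, 5.7% to 5.9% at n=20 and 5.3% to 5.4% at n=50. The t-test on the same data gave 4.85% to 5.12% throughout, so the t-test restores the level.

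**Which n applies.** SAP 7.9.4 does not say that the test is run by age version. Two features point that way: the summaries are by population, and raw totals with ranges ±18, ±30 and ±36 share no common scale on which to pool them. The planned total is 306 enrolled, split over three versions in unknown proportions. The per-protocol set, which requires at least 70% of time in Auto Mode, is also used for all endpoints and could reduce a group further.

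**Sample size.** The planned 245 pairs come from TIR alone. With the protocol's SD of 16 and correlation 0.5, the SD of the difference is √(16² + 16² - 2 × 0.5 × 16²) = 16. The normal formula gives (16 × 2.9265 / 3)² = 243.6, so 244, and the t-based calculation gives 245. No DTSQc quantity enters, so changing its test leaves the sample size alone.

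**The case against.** The strongest reply is that almost nothing depends on this. The SAP itself says the endpoint was not powered for testing, and the test supplements descriptive summaries. For secondary tests generally, "No adjustments for multiple comparisons will be performed", so a few tenths of a percentage point on one of them is minor. At n=100 the excess is under 0.2 points. All of this stands, and it sets the severity.

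A second reply is that the SAP switches to Wilcoxon for non-normal data. That limits how often the Z-test is used but does not repair it: the Z-test is the branch chosen when the data look normal, and a small group gives little power to detect non-normality. Protocol 12.3 has no such switch.

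Three stronger readings are tempting but not supported:

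- A reader might infer that the 5% level is certainly breached in the paediatric groups. The documents give neither the group sizes nor the variance source, and they do not state that testing is by age version, so the breach is conditional.
- A reader might infer that the DTSQc confidence interval will be too narrow. SAP 7.9.4 plans no interval for this score, and neither does the DTSQc paragraph of protocol 12.3.
- A reader might infer that every other continuous endpoint uses a t-test. TIR over time and the times below and above range use GEE, mixed or random-effects models (SAP 7.9.3 and 7.9.7). The contrast holds only for the paired mean-change tests.

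**Conclusion.** The point holds in a limited, conditional form. The named test is wrong as written, because it presupposes a known SD that the documents do not supply. The numerical consequence is small: about 0.2 points of excess one-sided error at n=100, 0.5 at n=30, 0.8 at n=20 and 1.7 at n=10.

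These figures rest on four assumptions: the SD is estimated from the sample, the 1.645 cut-off is used, the data are close to normal so that the Z branch applies, and n is the size of the group actually tested. In practice it matters only if an age group has fewer than about 20 to 30 subjects. It concerns one unpowered secondary test and is of the lowest severity.

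**What to change.** In SAP 7.9.4 and protocol 12.3, replace the Z-score test with a one-sample t-test of the total against 0. State that it is run separately within the adult, teen and parent versions. Keep the Wilcoxon signed-rank alternative in the SAP and add it to the protocol so that the two agree. Report the mean for each version with a t-based 95% confidence interval, as the SAP already does for its other mean changes.

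The cost is a few lines of wording. No data, visits or subjects are added. Protocol 12.3 asks for an amendment only when a principal feature of the study changes, so a SAP correction explained in the final report could suffice, with the protocol text aligned at its next revision.

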7.9.5. Quality of life based on DQoL

The objective is to evaluate the change from baseline in quality of life based on the DQoL evaluated at 6 and 12 months. The DQoL total scores will be calculated as the average across the four dimensions (satisfaction, impact, worries about future effects, worries about social effect). The DQoL questionnaire will be used and the mean scores will be compared between baseline and 6 and 12 months.

The different DQoL versions will be used to assess quality of life in the following populations:

- DQoL Adult (≥ 18 years old)
- DQoL Adult with Adolescent-oriented items (13-17 years old)
- No DQoL version and therefore no collection for patients 7-12 years old

The instrument has 49/46 core items forming four 5-point Likert scale according to the population:

- Satisfaction with treatment (18 items for adult with adolescent-oriented items and 15 for adult)
- Impact of treatment (20 items)
- Worries about future effects of diabetes (4 items)
- Worries about social and vocational issues (7 items)

The instrument also includes 1 generic health item that does not contribute to the scales.

Change from baseline in the DQoL total score will be analyzed at 6 months and at 12 months by means of paired (samples) t-test or Wilcoxon signed rank sum test according to the normal or non-normal distribution. In addition, the mean change will be displayed together with their 95% confidence interval (95%CI).

7.9.6. Fear of hypoglycemic events based on the Hypoglycemia Fear Survey (HFS)

The objective is to evaluate the change from baseline in the fear of hypoglycemic events based on the HFS evaluated at 6 and 12 months over the Study phase. The HFS questionnaire will be used and the mean scores will be compared between baseline and 6 and 12 months. The different HFS versions will be used to assess the fear of hypoglycemic events in the following populations:

- HFS Adult (≥ 18 years old)
- HFS Teen (13-17 years old)
- HFS Parent (7-12 years old)

The HFS Adult has 33 items for, 15 of them related to behavior and 18 related to worry.

The HFS Teen has 25 items for, 10 of them related to behavior and 15 related to worry.

The HFS Parent has 26 items for, 11 of them related to behavior and 15 related to worry.

All the items with scores: Never, Rarely, Sometimes, Often, Almost Always.

The total score per subject will be calculated as the sum of all item's scores and the average of the total score will be used for the comparison. The HFS total score will be analyzed by means of paired (samples) t-test or Wilcoxon signed rank sum test according to the normal or non-normal distribution. In addition, the mean change will be displayed together with their 95% confidence interval (95%CI).

7.9.7. Glycemic parameters

The objective is to evaluate the change in glycemic parameters at baseline and every three months until 12 months. The time of sensor glucose values below 70mg/dL and below 54mg/dL and the time of sensor glucose value above 180mg/dL and above 250mg/dL will be analyzed by means of GEE (generalized estimating equation) models or random effects models with random intercept as appropriate, for continuous outcomes to account for repeated measures using patient ID as the subject. The dependent variable will be pre-log transformed depending on normal or non-normal distribution. The model will have the glycemic parameter as dependent variable and baseline values and visits as explanatory variables. All assumptions for regression models will be assessed by viewing plots of the residual values. The plot for the mean change over time will be reported for the glycemic parameters and for graphical purpose only separately by population as deemed appropriate.

The HbA1c will be analyzed at 6 months and at 12 months by means of paired (samples) t-test or Wilcoxon signed rank sum test according to the normal or non-normal distribution. In addition, the mean change from baseline to 6 and 12 months, respectively, will be displayed together with their 95% confidence interval (95%CI).

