The objective of the run-in phase is to train the subjects on the MiniMed™ 780G insulin pump, assess subjects' compliance and ability to comprehend the study procedures and tolerance of wearing the sensor and transmitter continuously. It is expected that during the run-in phase the MiniMed™ 780G insulin pump will be set in Manual mode and all the algorithms are switched off, and baseline CGM data will be collected. Data from the MiniMed™ 780G insulin pump will be uploaded in the CareLink™ Personnel for Clinical Research as per standard practice before Auto Mode activation.

Baseline CGM data are listed below:

- Mean TIR (70-180mg/dL)
- Mean Time spent of sensor glucose value below 70mg/dL and below 54mg/dL
- Mean Time spent of sensor glucose value above 180mg/dL and above 250mg/dL
- Number of bio-chemical hypoglycemic event per week

Bio-chemical hypoglycemic events are defined as events with sensor glucose values lower than 54 mg/dL for more than 15 min consecutively.

The expected duration of the run-in phase is approximately 2 weeks. At the end of the run-in phase the MiniMed™ 780G insulin pump will be set in Auto Mode and the date of activation will be collected, and identified as a start of the study phase.

10.4. 6- and 12-month Follow-up Visits

Subsequent follow-up visits will be performed according to the therapy management standard of care at 6 and 12 months after Auto Mode activation in the study.

During the follow-up visits, patients will be asked to fill-out the following questionnaires:

Table 4: Questionnaires to be completed

	6 Month FU	12 Month FU
DTSQs	✓	✓
DTSQc	✓	
DQoL	✓	✓
HFS	✓	✓

All questionnaires have been designed for self-completion. When available (e.g. DTSQ and HFS), specific version of the questionnaires will be completed by a parent for subjects younger than 13 years old. DQOL will not be administered in case patient is between 7 and 12 years old. Patient questionnaires are in a paper form and should be completed on site during routine follow-up visits. It is recommended to administer the DTSQs before the DTSQc.

Patients are followed per standard of care, therefore there are no mandatory visit windows defined in this study, however the visit windows defined below are provided as recommendation and guidance.

- 6 Month FU: Follow-up Office Visit - 180 Days (\pm 45 days)
- 12 Month FU: Follow up Office Visit - 365 Days (\pm 45 days)

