12.1. Sample size justification

The primary endpoint is to evaluate if the MiniMed™ 780G therapy in Auto Mode increases the proportion of Time In Range (TIR) at 6 months compared to the MiniMed™ 780G therapy in manual mode at baseline. The endpoint is the Time In Range (TIR) defined as the proportion of sensor glucose concentration within the target range 70-180 mg/dL (3.9-10.0 mmol/L).

The Pivotal study [12, 13] enrolled adolescents (ages 14–21 years) and adults (ages 22–75 years) with type 1 diabetes in a multicenter pivotal trial. The Medtronic MiniMed™ 670G system was used during a 2- week run-in phase without HCL control, or Auto Mode, enabled (Manual Mode) and, thereafter, with Auto Mode enabled during a 3-month study phase. The study has shown a significant

improvement on TIR of 60.4% (10.9%) to 67.2% (8.2%) in adolescents and from 68.8% (11.9%) to 73.8% (8.4%) in adults. Using this information and considering that this study is expected to include around 32 sites and including also patients aged >7 years old, a lower increase of TIR and higher variability are expected. The following assumptions were made:

- Improvement in TIR of at least 3% points at 6 months compared to the baseline.
- Standard deviation as 16% due to the mixed population and multiple sites expected for this study.

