7.7. Treatment Characteristics

Duration of Study Exposure will be measured in days starting from the point of enrollment (informed consent signed and inclusion/exclusion criteria confirmed) through and including the time of study exit. The study has two phases:

The Run-In phase starts at the Enrolment (Consent date) and it ends at the Auto Mode activation date. It is expected that the Run-In phase will last 2 weeks.

The Study phase starts at the Auto Mode activation (end of Run-In phase) and it ends at 12 month follow up. The study phases exposures are calculated as:

- Duration of study exposure (days) = (Study Exit date – date of Enrollment(Consent) +1).
- Duration of Run-In phase exposure (days) = (date of Automode Activation – date of Enrollment(Consent) +1).
- Duration of Study phase exposure (days) = (date of Study exit – date of Automode Activation +1).

Extent of study exposures will be presented in a summary table.

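### SAP 7.9.7 permits a random-intercept model and leaves the role of the run-in open; if the run-in is a response row, standard errors for change from baseline can be too small

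*SAP*

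**What the plan says.** SAP 7.9.7 covers four sensor outcomes: time below 70 and 54 mg/dL and above 180 and 250 mg/dL. It offers "GEE (generalized estimating equation) models or random effects models with random intercept as appropriate". No working correlation, residual covariance or type of SE (model-based or robust) is named.

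The role of baseline can be read in two ways. The model sentence makes it a covariate: "The model will have the glycemic parameter as dependent variable and baseline values and visits as explanatory variables". The objective treats it as a time point: "The objective is to evaluate the change in glycemic parameters at baseline and every three months until 12 months". The parallel TIR section, SAP 7.9.3, counts baseline among the repeated observations, "The analysis will use multiple data points per patient (baseline, 3, 6, 9 and 12 months", and also puts baseline values in the model. It allows GEE or mixed models without mentioning a random intercept. For TIR change over time, Protocol 12.3 says the outcome "will be analyzed by means of mixed models for repeated measures".

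The baseline period differs in kind from the rest. Protocol 10.3 expects that during the run-in the "insulin pump will be set in Manual mode and all the algorithms are switched off", and SAP 7.7 says "It is expected that the Run-In phase will last 2 weeks". The later periods are three months each in Auto Mode. Protocol 12.1 cites pivotal TIR results, mean (SD), from Manual to Auto Mode: "60.4% (10.9%) to 67.2% (8.2%) in adolescents and from 68.8% (11.9%) to 73.8% (8.4%) in adults".

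**The concern.** A model whose only random term is a patient intercept, with independent equal-variance residuals, implies compound symmetry: the same variance in every period and the same correlation between every pair. A two-week open-loop period and four three-month closed-loop periods are unlikely to meet that. The pivotal TIR SDs are larger in Manual than in Auto Mode, and successive Auto Mode quarters may well resemble each other more than they resemble the run-in. The model averages over these differences. Comparisons with baseline, the ones of interest, can then get too small an SE, and comparisons between quarters too large a one.

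SAP 7.2 sets tests at one-sided 0.05 without multiplicity adjustment. Adverse events are not collected (Protocol 10.8), so time below 70 and 54 mg/dL carries much of the evidence on hypoglycemia, in a study meant to support reimbursement (Protocol 4.2).

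**Working it through.** **The plan's own figure.** The documents give none for the 7.9.7 models. The only related figure is 245 pairs for the primary TIR test. With the protocol's SD of 16 and correlation 0.5, the SD of the difference is 16 × √(2 × (1 − 0.5)) = 16. The normal formula gives (16 × (1.645 + 1.282) / 3)² = 243.6, and the t-based calculation gives 245, so it reproduces. The SAP's SD of 14 would give 188; that conflict is a separate matter. Here 245 serves only as the number of patients, and the ratios below do not depend on it.

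**Inputs.**
- Run-in/quarter correlation r0 = 0.5 (Protocol 12.2, SAP 6).
- TIR SDs, run-in/Auto Mode: 11.9/8.4 and 10.9/8.2 (Protocol 12.1), or 16/16 (Protocol 12.2).
- Quarter-to-quarter correlation rq: not in the documents, so assumed and varied from 0.3 to 0.9.

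**Formula.** Take five response rows per patient and complete data.
- True variance of a run-in/quarter difference: Vb = s0² + sq² − 2·r0·s0·sq.
- True variance of a quarter/quarter difference: Vq = 2·sq²·(1 − rq).
- The random-intercept residual variance is mean variance minus mean covariance. Twice that, the model's variance for any difference between two periods, is the average over all ten pairs: (4·Vb + 6·Vq)/10.
- SE ratio (model/true) for change from baseline: √(0.4 + 0.6·Vq/Vb).
- Actual one-sided error: 1 − Φ(1.645 × ratio).

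The SE is too small exactly when Vq is less than Vb.

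**Worked cases.**
- SD 16/16, rq 0.8: Vb = 256 and Vq = 2 × 256 × 0.2 = 102.4. Ratio = √(0.4 + 0.6 × 0.4) = 0.80. Error = 1 − Φ(1.316) = 9.4%.
- SD 11.9/8.4, rq 0.5: Vb = 141.61 + 70.56 − 99.96 = 112.21 and Vq = 70.56. Ratio = √(0.4 + 0.6 × 0.629) = 0.88. Error = 7.3%.

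**Ratio (one-sided error).**

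| rq | SD 16/16 | SD 11.9/8.4 | SD 10.9/8.2 |
|---|---|---|---|
| 0.3 | 1.11 (3.4%) | 0.96 (5.7%) | 0.99 (5.1%) |
| 0.5 | 1.00 (5.0%) | 0.88 (7.3%) | 0.90 (6.9%) |
| 0.7 | 0.87 (7.6%) | 0.79 (9.6%) | 0.81 (9.2%) |
| 0.8 | 0.80 (9.4%) | 0.74 (11.1%) | 0.75 (10.8%) |
| 0.9 | 0.72 (11.8%) | 0.69 (12.8%) | 0.70 (12.6%) |

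For the pivotal SDs at rq 0.7 to 0.9, a nominal 95% interval covers 82% to 89%, and SEs between quarters are 1.25 to 1.94 times too large. With the SDs reversed (8.4 run-in, 11.9 Auto Mode) and rq 0.5, the ratio is 1.08, so the SE is too large.

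**Check by simulation** (245 patients, SD 16, r0 0.5, rq 0.8). The true SE is 1.022. The five-row random intercept gave 0.818, and still 0.818 with baseline added as a covariate. Exchangeable GEE with robust SE gave 1.024 and the paired difference 1.026. The two methods that 7.9.7 offers side by side can therefore report materially different precision on the same data.

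**The case against.** The strongest reply is that the defect is conditional at every step.

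- *Role of baseline.* The 7.9.7 model sentence names baseline only as an explanatory variable. The five-point wording is in 7.9.3, which does not mention a random intercept. If baseline is a covariate only, the run-in lies outside the covariance structure and this mechanism disappears. This stands, but the 7.9.7 objective leaves the other reading open.
- *Direction.* A reader might infer that SEs for change from baseline are too small as a matter of course. The documents do not support that. They give no SDs or correlations for these four outcomes and no quarter-to-quarter correlation for any outcome, and some cells of the table show an SE that is correct or too large.
- *Proxy.* The pivotal SDs are for TIR on the raw scale with an earlier system. The plan's own sample size assumes equal SDs at both times, and 7.9.7 allows a log transformation. This stands: the figures illustrate and do not predict.
- *Alternatives in the plan.* GEE is listed first and is unaffected if robust SEs are used, but the SAP does not say that they will be. Residual plots are planned. They can show unequal variance but not unequal correlation, and no action is tied to them.
- *Consequence.* For these four outcomes 7.9.7 promises a plot of mean change. Its confidence-interval sentence concerns HbA1c. The exposure is therefore mainly in the tests under SAP 7.2, and in the intervals of 7.9.3 if its mixed model takes the same form.

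**Conclusion.** The concern holds in conditional form. SAP 7.9.7 permits a model that can understate the SE of change from baseline, and leaves open the choice that decides whether it does: the role of the run-in.

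Three conditions are needed together: a random intercept is chosen, the run-in is a response row, and run-in/quarter differences vary more than quarter/quarter differences. Under the pivotal TIR SDs the one-sided error would then be about 7% at a quarter-to-quarter correlation of 0.5, and 9% to 13% at an assumed 0.7 to 0.9, against a nominal 5%. Under equal SDs of 16 there is no understatement at 0.5 or below.

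Only secondary analyses are exposed: the four outcomes of 7.9.7, and possibly TIR over time in 7.9.3. The primary endpoint and HbA1c use paired tests in the SAP and are not touched.

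**What to change.** In SAP 7.9.7, and likewise in 7.9.3, replace the random-intercept option with one pre-specified model that has visit as a categorical factor, and give baseline a single role:

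- (a) run-in and four quarters as response rows, unstructured covariance (15 parameters), with baseline values removed from the explanatory variables; or
- (b) only the four quarters as response rows, baseline as covariate, unstructured covariance (10 parameters).

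GEE with robust (sandwich) SEs is an acceptable alternative if named as such, again with one role for baseline.

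Changing the covariance alone is not enough. If baseline is both a response row and a covariate with a common slope, a slope of 1 makes every baseline residual zero, and the likelihood under an unstructured covariance is unbounded.

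One point bears on the choice. Model (b) evaluates change at the observed mean baseline and treats that mean as fixed. With SD 16, correlation 0.5 and 245 patients, its SE is about 16 × √(1 − 0.25) / √245 = 0.885, against 16 / √245 = 1.022 when sampling of the baseline mean is counted. If mean change in the wider population is the target, (a) is the safer choice.

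The cost is a sentence or two in each section and a different covariance statement in the program. About 245 patients should suffice to estimate either covariance matrix. Change-from-baseline intervals may become somewhat wider.
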